6.5 Treating the patient

Patients enrolled in this study will receive our normal standard of post-transplant follow up care.

6.5.1 Patient numbering

As this is an open-label study there will be no blinding and thus no need for patient identifying numbers as part of a blinding strategy.

6.5.2 Dispensing the study drug

As this is an open-label study utilizing currently commercially available drugs, the drugs under study will be dispensed utilizing standard operating procedures.

6.5.3 Study drug supply, storage and tracking

As this is an open-label study utilizing currently commercially available drugs, special arrangements for study drug supply, storage and tracking will not be necessary.

6.5.4 Permitted study drug dose adjustments and interruptions

Zortress and Sirolimus dose adjustments and interruptions will be allowed and will be made at the discretion of the treating physician. All drug adjustments and interruptions will be recorded and monitored for this study, which requires little additional effort as this is already our current practice.

6.5.5 Study drug discontinuation and premature patient withdrawal

As we currently do for Sirolimus, Zortress dosing will be decreased or discontinued when the transplant physician deems appropriate due to deleterious side effects or the presence of infection or malignancy where a reduction in overall immunosuppression is desirable.

6.5.6 Early study termination

Early study termination will be considered if there is a statistically significant difference in primary outcome between the 2 study arms and it is the opinion of the treating physicians that this is likely due to differences in efficacy

7 **Visit schedule and assessments**

Table 7-1 lists all of the assessments and indicates with an “x” the visits when they are performed.

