8.1 Adverse events

Adverse events that the investigators consider to be clinically significant and associated with the use of Zortress® or Rapamune® will be recorded at each study visit. Serious adverse events will be reported to Novartis within 24 hours of discovery or notification. An adverse event will be considered serious if it results in any of the following outcomes:

- Results in death,
- Is life threatening (an adverse event is considered “life-threatening: if, in the view of the investigator, its occurrence places the subject at immediate risk of death. It does not include an adverse event that, had it occurred in a more severe form, might have caused death),
- Results in persistent or significant disability/incapacity, or substantial disruption of the ability to conduct normal life functions,
- Results in congenital anomaly, or birth defect,
- Requires inpatient hospitalization or leads to prolongation of hospitalization (hospitalization for treatment/observation/examination caused by AE is to be considered as serious).
- Other medically important events

Follow-up information for serious adverse events will be collected, recorded, and reported to Novartis.

Adverse events that meet IRB reporting requirements will be submitted to the IRB for review.

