8.2 Serious adverse event reporting

To ensure patient safety, every SAE, regardless of suspected causality, occurring after the patient has provided informed consent and until 30 days after the patient has stopped study participation (defined as time of last dose of study drug taken or last visit whichever is later).

Any SAEs experienced after this 30 day period should only be reported to Novartis if the investigator suspects a causal relationship to the study drug.

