10.2.2 Safety

Safety will be assessed by reviewing hospital admissions and graft and patient survival on a monthly basis as we currently do for our center's quality assurance reviews. Any apparent differences in outcome showing a disadvantage to the patient's in the Zortress group will be reviewed by our Renal Transplant surgical and medical directors and they will decide if the study needs to be halted or amended.

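### SAEs are collected but never brought by arm to the directors who can halt or amend the trial, and sections 6.5.6, 10.2.2 and 10.5 do not agree on whether study-level termination covers safety

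*Combined protocol and SAP*

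**What the plan says.** Three sections bear on stopping or changing the study.

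- **6.5.6 Early study termination** has two joined conditions. The first is statistical: "Early study termination will be considered if there is a statistically significant difference in primary outcome between the 2 study arms". The second is a judgement about cause, required in addition to the test result: "it is the opinion of the treating physicians that this is likely due to differences in efficacy".
- **10.2.2 Safety** sets the regular review: "Safety will be assessed by reviewing hospital admissions and graft and patient survival on a monthly basis". Its trigger is "Any apparent differences in outcome showing a disadvantage to the patient's in the Zortress group will be reviewed". The renal transplant surgical and medical directors receive the matter, and "they will decide if the study needs to be halted or amended".
- **10.5 Interim analysis** schedules a look at 6 months post-transplant for patient safety. It names no safety variable and no decision rule. The only outcome it mentions is the primary endpoint, for which non-inferiority is expected.

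Two sections govern serious events. Section 8.1 states: "Serious adverse events will be reported to Novartis within 24 hours of discovery or notification". Adverse events that meet IRB requirements also go to the IRB. Section 8.2 defines the scope as "every SAE, regardless of suspected causality, occurring after the patient has provided informed consent and until 30 days after the patient has stopped study participation". One of the six criteria for seriousness in 8.1 is "Requires inpatient hospitalization or leads to prolongation of hospitalization".

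Section 10.1.2 lists the safety data for analysis as patient and graft survival, biopsy-proven rejection and hospital admissions. SAEs are not in that list.

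**The concern.** The title names adverse events and tolerability among the comparisons. Section 1 says that no data exist on Zortress with Neoral in a steroid-free maintenance regimen after Thymoglobulin. A trial with that purpose would be expected to show its cumulative SAEs by arm to whoever can stop it.

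As written, the SAE stream leaves the center for the funder and, where required, the IRB. The monthly review works from a different and shorter list. Meanwhile 6.5.6 frames termination around efficacy alone, although the primary composite counts deaths (graft survival is not death-censored). A significant excess of deaths or graft losses that physicians attributed to toxicity would not meet its second condition.

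At stake is an imbalance in serious but non-fatal harm that builds up with no scheduled by-arm look. The transplant stay matters most: the mTOR drug starts on POD 0 and Thymoglobulin on POD 1, before any readmission is possible.

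**Working it through.** The documents give no alpha, boundary or power figure to reproduce, so the check is mainly textual.

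**Step 1. Compare the three provisions.**

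| Section | Data used | Trigger | Decided by |
|---|---|---|---|
| 6.5.6 | Primary composite | Significant difference, attributed to efficacy | Treating physicians give the attribution; decision-maker not stated |
| 10.2.2 | Admissions, graft survival, patient survival | Any apparent Zortress disadvantage; no significance or attribution needed | Surgical and medical directors |
| 10.5 | No safety variable named | None stated | Not stated |

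None lists SAEs. Section 10.2.2 is the broadest in practice but looks in one direction: an excess of deaths on Rapamune attributed to toxicity meets the wording of neither 6.5.6 nor 10.2.2.

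**Step 2. Map the six SAE criteria of 8.1 to the three items in 10.2.2.**

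| Criterion in 8.1 | Reaches the monthly review? |
|---|---|
| Death | Yes, through patient survival |
| Hospitalization or its prolongation | New admission: yes. Prolonged transplant stay: only if that stay and its length count under admissions |
| Life-threatening | Only if it also causes an admission, graft loss or death |
| Disability or incapacity | Same condition |
| Congenital anomaly or birth defect | Same condition |
| Other medically important event | Same condition |

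One criterion is fully covered, one partly, and four have no route of their own.

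**Step 3. See whether another section closes the gap.** Section 6.5.5 acts on side effects in the individual patient, not the study. Table 7-1 schedules adverse events from Day 0 to month 36, so the data should exist, but it sets no review. The safety list in 10.1.2 omits SAEs.

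**Step 4. How high a bar is 6.5.6?** Inputs: 60 patients randomized 2:1, so 60 × 2/3 = 40 Zortress and 60 × 1/3 = 20 Rapamune. Assumptions: uncorrected chi-squared test, two-sided 0.05, all 60 patients evaluable. As a stand-in for the control composite, take 2/20 = 10%, the top of the 7% to 10% first-year rejection range in section 1. With y Zortress events,

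z = (y/40 − 2/20) / √[p(1 − p)(1/20 + 1/40)], where p = (y + 2)/60.

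- y = 13: p = 0.250, z = 0.225/0.1186 = 1.90, not significant.
- y = 14: p = 0.267, z = 0.250/0.1211 = 2.06, significant.

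So 14/40 = 35% against 10% is needed before the first condition of 6.5.6 is met. Early warning therefore rests on 10.2.2, and what that review is shown matters.

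**Step 5. Why by arm with denominators.** Under 2:1 allocation a common SAE risk r gives 40r patients on Zortress and 20r on Rapamune, twice as many with no true difference. Raw counts would mislead; patients with at least one SAE over patients randomized would not.

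**The case against.** The strongest reply is that 10.2.2 already does most of the work. It meets monthly, needs neither significance nor a view on cause, and covers non-fatal graft loss and any toxicity that leads to admission. This stands. A reader might infer that no written rule acts on non-fatal toxicity; 10.2.2 shows otherwise.

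A reader might also infer that 6.5.6 forbids stopping for safety. It does not: it states when termination will be considered and does not exclude other grounds. Excess Zortress deaths or graft losses attributed to toxicity would still reach the directors through 10.2.2.

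A third tempting reading is that oversight is blind in the early post-operative period. That too goes beyond the text. Deaths and graft losses in that window are reviewed, and the admissions item does not expressly exclude the transplant stay or its length. The gap for prolonged transplant stays is therefore conditional on how admissions is read.

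It can also be said that 10.2.2 refers to differences in outcome generally, that 10.5 adds a safety look, and that staff at one center in an open-label trial will know of serious events. The first follows directly on a three-item list and is most naturally read as referring to it. The second names no safety content. The third is probably true, but knowing of individual cases is not a cumulative comparison by arm, and none is written.

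**Conclusion.** The point holds in a limited form. Every SAE falls within the scope of 8.2, yet no section takes SAEs by arm to the directors who can halt or amend. Serious toxicity without a hospital admission, graft loss or death has no written route to study-level review. SAEs that only prolong the transplant stay share that gap if the stay is not counted as an admission. Separately, 6.5.6, 10.2.2 and 10.5 give different accounts of what study-level termination covers.

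The number of patients affected cannot be stated: the documents give no SAE rates, and an assumed rate common to both arms would show no missed imbalance. The conclusion rests on the text alone and not on the illustration for 6.5.6. It is a worthwhile and inexpensive improvement to oversight, not evidence that the trial lacks a safety halt route.

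**What to change.** 1. In 10.2.2, add to the existing monthly review a cumulative table by arm of all SAEs collected under 8.2: patients with at least one SAE over patients randomized, expressly including SAEs that prolong the transplant stay. The same directors review it.
2. In 10.5, name the same table as an input to the 6-month look.
3. Reconcile 6.5.6, 10.2.2 and 10.5 on whether study-level termination covers safety as well as efficacy. The criterion itself is for the sponsor and investigator to set.

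The cost is one table from data already collected, for a meeting that already takes place, plus the wording changes. No new committee is needed. The downside is slightly more preparation each month and some chance imbalances to discuss, which is to be expected with about 40 and 20 patients.

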7.1 Table 7-1

Assessment schedule:

Visit number	1 Screening/ Baseline	2	3	4	5	6	7	8	9	10	11	12	13	14	15	16	17	18
Time of Visit		Day 0	Day 1	Day 2	Day 3	Day 4	Day 5 ¹	Day 6 ¹	Day 7 ¹	Wk 2	Mo 1	Mo 2	Mo 3	Mo 6	Mo 12	Mo 18	Mo 24	Mo 36
Inclusion/Exclusion criteria	X																	
Informed consent	X																	
Physical examination	X	X	X	X	X	X	X	X	X	X	X	X	X	X	X	X	X	X
Demographics	X																	
Medical History	X																	
Pregnancy Test ²	X																	
Vital signs	X	X	X	X	X	X	X	X	X	X	X	X	X	X	X	X	X	X
Hematology		X		X				X	X	X	X	X	X	X	X	X	X	X
Chemistry		X			X			X	X	X	X	X	X	X	X	X	X	X
Lipid panel	X									X	X	X	X	X	X	X	X	X
24 hour urine												X	X	X	X	X	X	X
Alloscreen	X															X		
Flow Crossmatch	X															X		
HGB A1C																X		X
Kidney Biopsy	X															X		
Adverse events		X	X	X	X	X	X	X	X	X	X	X	X	X	X	X	X	X
Cyclosporine level ³				X				X	X	X	X	X	X	X	X	X	X	X
Everolimus level ³					X			X	X	X	X	X	X	X	X	X	X	X
Optional sub study: Plasma for Biomarkers ⁴	X				X			X	X	X	X	X	X	X	X	X	X	X

Legend:

- 1: If still inpatient
- 2: Females capable of childbearing
- 3: Cyclosporine and Zortress levels are monitored twice weekly for 0-3 months post-transplant, every two weeks for 3-12 months post-transplant, and monthly greater than 1 year post-transplant.
- 4: Plasma for biomarkers will be assessed at the University of Colorado in a subset of patients using existing plasma samples.

Patients will be followed as per the standard of care at this transplant center (The Ohio State University Medical Center, Division of Transplantation). Additional study procedures include a protocol biopsy at month 12 and some additional laboratory work at screening/baseline and at months 6, 12, 24, and 36.

7.2 Information to be collected on screening failures

No information will be collected on patients failing the screening process.

7.3 Patient demographics/other baseline characteristics

Patient demographics are routinely captured within our transplant database and as such will be available for analysis. Demographic data collection includes, but is not limited to, name, age, gender, race, cause of renal failure, years on dialysis, sensitization status (PRA),

7.4 Treatment exposure and compliance

Zortress serum trough levels will be monitored twice weekly for the first 3 months after transplant, once weekly between months 3 and 6, every other week between months 6 and 12, and monthly thereafter. Compliance with Zortress can be determined based on serum trough levels.

7.5 Efficacy

7.5.1 Efficacy assessment 1

- Incidence of graft loss in the first post-transplant year
- Incidence of patient death in the first post-transplant year
- Incidence of biopsy proven acute rejection at 1 year post-transplant
- Tolerability of Zortress at 1 year post-transplant
- Renal function at 1 year post-transplant

8 Safety monitoring

8.1 Adverse events

Adverse events that the investigators consider to be clinically significant and associated with the use of Zortress® or Rapamune® will be recorded at each study visit. Serious adverse events will be reported to Novartis within 24 hours of discovery or notification. An adverse event will be considered serious if it results in any of the following outcomes:

- Results in death,
- Is life threatening (an adverse event is considered “life-threatening: if, in the view of the investigator, its occurrence places the subject at immediate risk of death. It does not include an adverse event that, had it occurred in a more severe form, might have caused death),
- Results in persistent or significant disability/incapacity, or substantial disruption of the ability to conduct normal life functions,
- Results in congenital anomaly, or birth defect,
- Requires inpatient hospitalization or leads to prolongation of hospitalization (hospitalization for treatment/observation/examination caused by AE is to be considered as serious).
- Other medically important events

Follow-up information for serious adverse events will be collected, recorded, and reported to Novartis.

Adverse events that meet IRB reporting requirements will be submitted to the IRB for review.

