Enrollment	Point/time of patient entry into the study; the point at which informed consent must be obtained (i.e. prior to starting any of the procedures described in the protocol)
Investigational drug	The study drug whose properties are being tested in the study; this definition is consistent with US CFR 21 Section 312.3 and is synonymous with "investigational new drug."
Medication number	A unique identifier on the label of each medication package in studies that dispense medication using an IVR system
Patient number	A number assigned to each patient who enrolls in the study. When combined with the center number, a unique identifier is created for each patient in the study.
Stage	A major subdivision of the study timeline; begins and ends with major study milestones such as enrollment, randomization, completion of treatment, etc.
Period	A minor subdivision of the study timeline; divides phases into smaller functional segments such as screening, baseline, titration, washout, etc.
Premature patient withdrawal	Point/time when the patient exits from the study prior to the planned completion of all study drug administration and assessments; at this time all study drug administration is discontinued and no further assessments are planned
Randomization number	A unique identifier assigned to each randomized patient, corresponding to a specific treatment arm assignment
Stop study participation	Point/time at which the patient came in for a final evaluation visit or when study drug was discontinued whichever is later
Study drug	Any drug administered to the patient as part of the required study procedures; includes investigational drug and any control drugs
Study drug discontinuation	Point/time when patient permanently stops taking study drug for any reason; may or may not also be the point/time of premature patient withdrawal
Variable	Information used in the data analysis; derived directly or indirectly from data collected using specified assessments at specified timepoints

Protocol synopsis

Title of study: A prospective, randomized, single center pilot study comparing patient and graft survival, adverse events and tolerability of Zortress® (everolimus) versus Rapamune® (sirolimus) in combination with low dose Neoral® (cyclosporine) dosed by C2 monitoring, in deceased and living donor renal transplant recipients under a Thymoglobulin® (antithymocyte globulin) and rapid steroid induction protocol.

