Two prospective randomized trials (A2306 and A2307) have demonstrated that everolimus combined with steroids and low dose Neoral with (A2307) or without (A2306) basiliximab induction result in excellent 1 year outcomes (1). In 2002 we adopted an immunosuppressive regimen using Rapamune and reduced dose Neoral without steroids using induction therapy with Thymoglobulin. Since employing this regimen our acute rejection rate within the first year post-transplant has been between 7% and 10% for any given calendar year. However, many patients need to have their Rapamune discontinued due to drug related side effects or compliance difficulties related to the noon dosing (when most other medications are taken at 8 am and 4 pm). We feel strongly that use of an alternative drug to Rapamune in such cases is necessary. Use of Zortress in this setting would be ideal, however, no data currently exists concerning the use of Zortress with Neoral in a steroid free maintenance immunosuppression regimen following Thymoglobulin induction. Thus we propose this pilot study primarily to verify Zortress efficacy using our established immunosuppressive protocol. Secondarily we are interested in characterizing the Zortress drug related side effect profile to enable us in the future to exploit any favorable differences between Zortress and Rapamune.

2 Purpose and rationale

Our center's renal transplant immunosuppression protocol has consisted of Thymoglobulin and steroid induction for 5 doses only, with early initiation of Rapamune® (Sirolimus) and then Neoral for nearly a decade now. We do observe a significant amount of adverse events in our patient population, with many of these potentially related to the Sirolimus. The combination of "half-dose" cyclosporine (early C2 levels around 800 to 1000 ng/ml) allows us to minimize calcineurin inhibitor toxicity and its combination with the mTOR drug Sirolimus provides excellent protection against acute rejection in our renal transplant recipients. Our earlier experience with Everolimus and the recent publications describing renal recipients' outcomes with this drug, suggest to us that our patients may do better on Everolimus than Sirolimus (1,2). For our center, this pilot study would be very straightforward as the only difference in medication from our current well established protocol would be the randomization to either Rapamune®, our current standard of care, or Zortress®, the study drug.

3 Objectives

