3.2 Secondary objectives

Secondary outcomes would include factors involved with adverse events and tolerability and would include: renal graft survival (non-death censored) and biopsy proven acute rejection at 6 months, 2 and 3 years, as well as the number and grade of acute rejection episodes and responsiveness to treatment, serum creatinine and estimated GFR, results of renal biopsies at 12 months post-transplant to look for histological evidence of graft injury, early and late wound complications, infections including CMV, EBV and BK infections as monitored by serum PCR testing, lipid panel testing, particularly triglycerides, cardiac events such as acute myocardial infarctions or Congestive Heart Failure episodes, and tolerability of the Neoral and mTOR combination as determined by the patients who required conversion off of the intended randomized drug combination, with attempt to document why the patient did not tolerate the drug combination. All objectives are exploratory in nature as this is a pilot study.

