3.3 Exploratory objectives

4 To explore the kidney and vascular endothelial function assessed by a panel of molecular markers over the observation period. Study design

Randomized, single center parallel-group, open-label study.

Pilot study with exploratory objectives.

Eligibility: All primary or retransplant recipients of deceased donor or living donor grafts with negative crossmatch who are felt to have good expectations for renal function recovery after surgery will be offered entry into the study.

Treatment scheme is as described above, with Solumedrol 500 mg IV in OR as induction, then 5 doses of Thymoglobulin starting morning of POD 1 at 1.25 mg/dose (rounded to nearest 25 mg) with rapid steroid taper over five doses. The mTOR inhibitor drug will be started on POD 0 and Neoral introduced as renal function recovers, usually starting on POD 2.

Measurement/Assessments: as described above, graft and patient survival per standard definitions, clinically indicated biopsies for determination of acute cellular or antibody mediated rejection, renal function as estimated from serum Cr based on MDRD, clinic visits for wound assessment, standard of care labs for renal function, bone marrow function (WBC and platelet count), liver function, lipid panel, donor specific antibody determination during any significant increase in serum Cr, drug levels routinely monitored for need of number of dose adjustments and compliance, Emergency Room and hospitalizations, as well as unscheduled clinic and other physician visits. For the pilot study, we would perform scheduled CMV, EBV and serum BK PCRs monthly for the first year, then quarterly or with any viral symptoms.

A subset of patients will have coded plasma samples sent to clinical research and development at the University of Colorado. These biomarker samples will be used to assess vascular endothelial dysfunction and inflammation markers as well as kidney dysfunction markers.

Plasma samples are collected and stored at The Ohio State University Wexner Medical Center tissue typing lab per standard of care.

5 Population

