6.4 Treatment blinding

This is an open-label study and thus there will be no blinding.

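### Non-serious adverse events outside the listed endpoints are recorded only if unblinded investigators attribute them to a study drug, so comparing them by arm risks attribution bias

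*Combined protocol and SAP*

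**What the plan says.** The recording rule in section 8.1 covers "Adverse events that the investigators consider to be clinically significant and associated with the use of" Zortress or Rapamune, at each study visit. On masking, section 6.4 says: "This is an open-label study and thus there will be no blinding".

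Two places point to a comparison of adverse events. The study title in the synopsis describes a study "comparing patient and graft survival, adverse events and tolerability of" the two drugs. Section 1 gives a secondary interest in "characterizing the Zortress drug related side effect profile to enable us in the future to exploit any favorable differences between Zortress and Rapamune".

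Much of the safety information is collected by routes that do not depend on the 8.1 judgement:

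- Section 8.2 covers every serious adverse event whatever its suspected cause.
- Section 3.2 opens with "Secondary outcomes would include factors involved with adverse events and tolerability" and lists specific outcomes, including wound complications, viral infections, lipids and cardiac events. It defines tolerability "as determined by the patients who required conversion off of the intended randomized drug combination".
- Section 6.5.4 states: "All drug adjustments and interruptions will be recorded and monitored for this study".
- Section 4 includes "Emergency Room and hospitalizations, as well as unscheduled clinic and other physician visits" among the assessments.
- Sections 10.1.2 and 10.2.1 list further endpoints with their own definitions. Section 10.1.2 names the safety data as survival, biopsy-proven rejection and hospital admissions.

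Neither 10.1.2 nor 10.2.2 names the records made under 8.1 as something to be analysed.

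**The concern.** The rule applies two judgements, importance and drug association, before an event is written down as an adverse event. Both are made with knowledge of the arm. An event judged unrelated or unimportant may leave a trace in examination, laboratory or visit data (Table 7-1, section 9.1), but not as an adverse event, and it may not be recoverable at analysis.

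The protocol itself gives reason to think attribution could differ between arms. Section 2 says the centre already regards many adverse events as possibly due to sirolimus and expects that patients may do better on everolimus; that could raise attribution in the Rapamune arm. Section 10.2.2 directs review only to disadvantages in the Zortress arm; that could raise attention there instead. Neither settles the direction.

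At stake is the part of the side-effect comparison that rests on these residual events. A pilot's side-effect profile is meant to inform later choices, and section 1 says so.

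**Working it through.** **Which events are affected.** Start with all adverse events and remove those captured elsewhere: serious events (8.2), conversions with their reasons (3.2, 10.2.1), dose changes and interruptions (6.5.4), listed endpoints (3.2, 10.1.2, 10.2.1), and emergency, hospital and unscheduled visits (4). What remains is a non-serious event that is not a listed endpoint and leads to no conversion, dose change or unscheduled contact. For these, 8.1 is the only recording rule. The adverse-events row in Table 7-1 sets when to ask, not what to record. No section provides common attribution criteria or masked adjudication.

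**Inputs.** From the documents: 60 patients randomised 2:1 (sections 5 and 6.2), hence 60 × 2/3 = 40 Zortress and 60 × 1/3 = 20 Rapamune. Assumed, because the documents give no figures: true incidence of these residual events, and the probability that an event is judged recordable in each arm. The plan has no figure of its own to reproduce.

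**Size of a spurious difference.** Recorded rate = true incidence × probability of attribution. With the same true incidence in both arms, the spurious difference = incidence × attribution gap.

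| True incidence (assumed) | Gap 10 points | Gap 30 points |
|---|---|---|
| 20% | 0.20 × 0.10 = 2 points | 0.20 × 0.30 = 6 points |
| 40% | 0.40 × 0.10 = 4 points | 0.40 × 0.30 = 12 points |
| 60% | 0.60 × 0.10 = 6 points | 0.60 × 0.30 = 18 points |

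The sign reverses if the gap reverses.

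**Size against sampling error.** SE = √[p₁(1−p₁)/40 + p₂(1−p₂)/20], with p₁ the recorded rate on Zortress and p₂ on Rapamune.

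| Incidence | Attribution, Zortress v Rapamune | Recorded rates | SE | Difference / SE |
|---|---|---|---|---|
| 20% | 50% v 60% | 0.10 v 0.12 | 0.087 | 0.23 |
| 60% | 50% v 80% | 0.30 v 0.48 | 0.133 | 1.35 |
| 60% | 10% v 40% | 0.06 v 0.24 | 0.103 | 1.75 |
| 60% | 40% v 10% | 0.24 v 0.06 | 0.086 | 2.10 |

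The last three rows share the same 18-point difference, yet the ratio runs from 1.35 to 2.10 according to the assumed attribution level. No ceiling in standard errors can therefore be stated.

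**False-positive rate, if tested.** The synopsis assigns chi-squared tests to any other dichotomous variable. Exact binomial enumeration of the uncorrected test at 40 v 20, with an assumed two-sided 5% level and equal true incidence, gives:

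| True incidence (assumed) | 60% v 80% attribution | 80% v 60% attribution |
|---|---|---|
| 30% | 8.9% | 7.1% |
| 50% | 12.5% | 11.7% |
| 70% | 18.6% | 18.6% |

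When attribution is equal in the two arms, the rate is 4.8% to 5.5% over the same incidences (attribution 70% or 100% in both).

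**The case against.** The strongest reply is that the harmed comparison is not in the analysis plan. The named safety data are survival, rejection and admissions, and the title's adverse-event comparison can be read as the section 3.2 list, none of which passes through the 8.1 filter. Section 1 asks for a drug-related profile, and attributed events are what such a profile consists of. The rule is worded identically for both drugs. Section 8.1 does not say that other events may not be recorded. The residual is narrowed further because other medically important events count as serious, and events meeting IRB requirements are submitted to the IRB. Finally, every magnitude is assumed, and three of the four standard-error cases fall below 2.

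Much of this stands. The problem is conditional on the 8.1 records being compared by arm, the affected class is limited, and the figures illustrate the mechanism without showing that it will occur. That recording is confined to attributed events is an inference, though a fair one, because nothing else requires these events to be recorded as adverse events.

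What does not stand is that identical wording protects the comparison: the same rule can be applied differently by people who know the arm. Nor does the section 1 aim argue for the filter. Its interest is in differences between the drugs, and a separate relatedness field keeps the drug-related profile while adding the all-cause rate needed to interpret it.

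**Conclusion.** The concern holds as a design weakness of limited reach. For non-serious adverse events outside the listed endpoints, recording depends on unmasked attribution, so a by-arm difference in those records could not be read as a difference in harm. The illustrative spurious difference is 2 to 18 points in either direction, resting wholly on assumed incidences of 20% to 60% and attribution gaps of 10 to 30 points; the documents establish neither its direction nor its size.

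This recording rule does not touch the primary composite, serious adverse events, tolerability as defined by conversion, or the listed endpoints. The study is declared exploratory and unpowered (sections 3.2 and 10.3). The change should be made because it is cheap and because events left unrecorded may not be retrievable later; the main result does not depend on it.

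**What to change.** In section 8.1, record all adverse events in both arms at the scheduled visits, whatever their suspected cause or judged importance, with relatedness and severity as separate fields. In section 10.2.2, add a descriptive by-arm comparison of all-cause adverse events, with attributed events as a supportive table. State as a limitation that differences in how events are elicited and reported in an open-label study would remain. The definitions of tolerability, serious adverse events and listed endpoints need no change.

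No visits or assessors are added. Table 7-1 already marks adverse events at all 17 post-baseline visits (visits 2 to 18), or 14 if the patient is discharged before Day 5. With full follow-up of 60 patients that is 14 × 60 = 840 to 17 × 60 = 1,020 checks already planned. The real cost is the extra entries and two fields at those checks, which the documents give no basis to estimate. Section 8.2 already applies the causality-free standard to serious events, so the change extends a standard that the protocol already uses.
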